9.4.3 ANALYSIS OF THE SECONDARY ENDPOINTS

We will use the definition of graft failure and displacement previously outlined by the Corneal Preservation Time Study (CPTS).⁵⁰ Graft failure will be defined as the occurrence of one of the following: 1) cornea which requires re-grafting for any reason; 2) cornea which remains cloudy [per the CPTS grading scale of recipient stroma clarity without clearing either if a) cloudy on the first postoperative day which does not clear within 8 weeks, or b) initially clear postoperatively but becomes and remains cloudy for 3 months.

CPTS Graft Failure Classification

- 1) Early: cloudy or equivocal recipient stroma on the first postoperative day that does not clear or requires a re-graft within 8 weeks and is associated with intra- and/or perioperative complications
- 2) Primary Donor: cloudy or equivocal recipient cornea on the first postoperative day that does not clear or requires a re-graft within 8 weeks in the absence of surgical complications*
- 3) Graft rejection: clouded recipient central stroma following an allograft reaction that was initially clear
- 4) Non-rejection: graft that had clear central recipient stroma on the first post-operative visit but becomes cloudy due to causes other than an immune event (e.g. surface failure, infection, glaucoma/hypotony, endothelial decompensation, interface irregularity/opacity, stromal scarring, blunt or penetrating trauma, or other causes
- 5) Refractive/visual: graft that requires re-grafting due to inadequate vision while the recipient central stroma is clear

DETECT

Version 5.0
21 March 2023

* Differs from EBAA Medical Standards which defines primary donor failure as a re-graft that is performed > than 8 weeks after keratoplasty.⁵¹

CPTS Graft displacement Classification

- 1) Donor positioning: recorded as centered, decentered, total dislocation in anterior chamber, total dislocation in posterior chamber
- 2) Partially detached: yes, no
- 3) If partially detached: central, peripheral, both & % of detachment: 0 to less than 25%, 25 to less than 50%, 50 to less than 75%, 75 to 100%

Other Secondary Outcomes.

Within each secondary outcome group, we will correct for multiple comparisons across the two factorial treatments using a Holm-Bonferroni approach to control the family-wise error rate.

In DETECT I, we will examine ECL at 12 months as a key secondary outcome for the UT-DSAEK versus DMEK comparison and will examine BSCVA at 12 months as a key secondary outcome for the ripasudil versus placebo comparison.

Vision-Related Quality of Life. VFQ will be compared between groups using the National Eye Institute Vision-Function Questionnaire 25 (NEI-VFQ-25) at 3 and 12 months controlling for 1-day VFQ. This will be conducted using linear regression with baseline and assignment variables. We estimate the study will be sufficiently large to detect a difference in NEI-VFQ of 4 points, assuming a 2-sided alpha of 5%, 90% power, 110 patients per group, outcome standard deviation of 10.1 and correlation between baseline and follow-up of 0.51 (standard deviation and correlation estimated from NEI-VFQ measurements in the DETECT pilot).⁵²

Endothelial cell morphology. We will use methods similar to the primary analysis for ECL to study the impact of ripasudil on the endothelial cell morphology by comparing the coefficient of variation (CV), variability in hexagonal cell shape (HEX) at the 3-month time point while still on ripasudil as well as at 6, 12 and 24 months after cessation of the study drug.

Pentacam Scheimpflug Tomography. Is a rotating scheimpflug camera, which provides 3 dimensional images of the cornea. In addition to topographic maps with keratometric readings of the anterior and posterior cornea, Pentacam reports on the total corneal power, corneal thickness maps, higher order aberrations and densitometry.

- *Higher order aberrations:* comparing the quantitative measure of irregular astigmatism, expressed in microns as the root mean square (RMS) of the Zernike polynomials across the pupil (approximately central 4 mm of the pupil) controlling for baseline measurements
- *Densitometry:* comparing a measure of corneal reflectance (i.e. scarring) in gray scale units controlling for baseline measurements
- Statistical analysis will be similar to that describe above, linear mixed effects regression using treatment assignment and baseline values as covariates, using the same template as we did for BSCVA.
- For a final supplementary analysis, we will also repeat the BSCVA analyses, but now including Pentacam densitometry at baseline as a predictor. We will report both the regression coefficient for baseline densitometry as a predictor, as well as the coefficient for treatment.

Cost-effectiveness analysis. A supplementary analysis will use individual-level cost outcomes as well as individual-level health outcomes. We propose to report standard cost-effectiveness acceptability curves based on bootstrap resampling at the individual level from both control and intervention subjects (for a statistical, clinical-trial based, cost-effectiveness analysis from a health care system perspective).⁵³ The outcome variable will be cost per line of vision gained.

Treatment allocation survey. We will perform a formal assessment of study participant masking as outlined in SAP 6.4.1

DETECT

Version 5.0
21 March 2023

Adverse Events. All adverse events, including the number of re-bubble procedures, graft failure and graft rejection will be tabulated and reported. Statistical comparisons will be conducted using Fisher's exact test, but with the caution that failure to find evidence of a difference cannot be used to infer a lack of risk difference for rare outcomes such as primary graft failure since the study is not powered to examine these.

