9.2 SAMPLE SIZE DETERMINATION

DETECT I

We will power the study for each comparison. For both primary analyses, we used a standard sample size formula based on an ANCOVA that conditions on a baseline outcome measure.⁴⁹ Given that endothelial cell density and visual acuity are different, non-correlated outcomes ($R=0.08$ in the DETECT pilot study) with different randomization, each will have its own alpha of 0.05. Specifically, we will be comparing:

- I. With 80 patients per group (160 total), we estimate that we will have at least 90% power to detect a difference in logMAR of 0.11 at 12 months, assuming an outcome SD of 0.2, a 2-sided alpha of 0.05, and 10% loss-to-follow-up. Under the same assumptions but 80% power, the minimum detectable difference in logMAR is 0.09. We assumed a higher SD in the calculation compared with the SD estimated in the DETECT pilot (adj. SD=0.147) to allow for more complex eyes enrolled in the trial.
- II. With 80 patients per group (160 total), we estimate that we will have at least 90% power to detect a 7% difference in ECL between enrollment and 12 months, assuming an outcome SD of 0.134 estimated from the DETECT pilot study, a 2-sided alpha of 0.05, and 10% loss-to-follow-up. If we assume a larger outcome SD for more complex eyes (SD=0.18), we will have at least 90% power to detect a 10% difference in ECL.

DETECT II

With 30 patients per group (60 total), we estimate that we will have at least 90% power to detect a difference in logMAR of 0.13, assuming an outcome SD of 0.147, a 2-sided alpha of 0.05, and 10% loss-to-follow-up. The SD was estimated from the DETECT pilot study and was adjusted for correlation between baseline and 12-month measurements (outcome SD = 0.163, correlation = 0.428, adjusted SD = 0.147). Under the same assumptions but 80% power, the minimum detectable difference is 0.11 logMAR.

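### The NEI-VFQ power statement assumes 110 patients per group, but the randomised comparisons have 80 (DETECT I) and 30 (DETECT II), so the stated 90% power for 4 points is not reached in either trial

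*Protocol*

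**What the plan says.** Protocol section 9.4.3, under vision-related quality of life, compares NEI-VFQ-25 between groups "at 3 and 12 months controlling for 1-day VFQ". It continues: "This will be conducted using linear regression with baseline and assignment variables". The trial size is then described as "sufficiently large to detect a difference in NEI-VFQ of 4 points". The inputs given for that claim are these: "assuming a 2-sided alpha of 5%, 90% power, 110 patients per group, outcome standard deviation of 10.1", together with a "correlation between baseline and follow-up of 0.51". The SD and correlation come from the DETECT pilot.

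Section 9.2 sizes the two trials separately. For each DETECT I comparison it says "With 80 patients per group (160 total", and for DETECT II "With 30 patients per group (60 total". Both statements allow for 10% loss to follow-up; the VFQ sentence gives no loss assumption.

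For secondary outcomes in general, section 9.4.3 says "we will correct for multiple comparisons across the two factorial treatments using a Holm-Bonferroni approach".

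**The concern.** The group size in the VFQ sentence matches neither trial. The only visible source is 160 + 60 = 220 study eyes, divided by two. Reaching 110 against 110 would mean pooling the trials in one of two ways:

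- all DMEK eyes (80 + 30) against UT-DSAEK and DSO eyes together (80 + 30);
- all ripasudil eyes (80 + 30) against all placebo eyes (80 + 30).

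The protocol describes neither. The trials have different eligibility criteria (section 5.1), different comparators and separate primary models (section 9.4.2). In DETECT II ripasudil goes only with DSO and placebo only with DMEK, so drug and surgery cannot be separated there.

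The figure matters because the VFQ result is meant to be interpreted. The objectives table in section 3 gives VFQ the role of showing whether differences in acuity or cell density are clinically relevant. Section 2.2 treats 4 points as a small but meaningful change, suggests that low power may explain why the pilot found no difference between arms, and regards the case for DMEK over UT-DSAEK as weaker if VFQ does not improve. Read against a stated 90% power, a null VFQ result would carry more weight than the design supports, most of all in DETECT II.

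**Working it through.** **Inputs**

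- Section 9.4.3: difference 4 points, SD 10.1, baseline-to-follow-up correlation 0.51, two-sided alpha 0.05, target power 90%, 110 per group.
- Section 9.2: 80 per group (DETECT I), 30 per group (DETECT II), 10% loss.

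**Formulas** (normal approximation, two equal groups, analysis adjusted for baseline)

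- Adjusted SD = 10.1 × √(1 − 0.51²) = 8.69
- SE = 8.69 × √(2/n)
- Power = Φ(4/SE − 1.960)
- Difference detectable with 90% power = (1.960 + 1.282) × SE

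**The protocol's own figure**

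With 110 per group less 10%, n = 99 and SE = 1.235. Power is 90.0% and the detectable difference is 4.00 points, which is the stated claim. With 110 and no loss, power is 92.7% and the detectable difference 3.80 points, which also satisfies it. Without baseline adjustment (SD 10.1), power would be 83.6% at 110 and 79.6% at 99, so the sentence evidently rests on the baseline-adjusted SD. The arithmetic is sound for 110 per group; the input is what fails.

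**The same calculation with the trials' group sizes**

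| Trial | n per group | SE | Power for 4 points | Detectable with 90% power |
|---|---|---|---|---|
| DETECT I, 10% loss | 72 | 1.448 | 78.9% | 4.69 |
| DETECT I, no loss | 80 | 1.374 | 82.9% | 4.45 |
| DETECT II, 10% loss | 27 | 2.364 | 39.4% | 7.66 |
| DETECT II, no loss | 30 | 2.243 | 43.0% | 7.27 |

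Using the t distribution lowers the two 10%-loss powers slightly, to 78.3% and 38.2%.

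**Multiplicity in DETECT I**

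Holm across the two factorial treatments tests the smaller p-value at 0.025 and, if that passes, the other at 0.05. At 0.025 with 72 per group, power is Φ(4/1.448 − 2.241) = 69.9%.

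**The covariate label**

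The schedule of activities (section 1.3) collects the questionnaire at Visit 1 (Day 0), month 3 and month 12. No day-1 score is scheduled. The sentence after the label names baseline as the covariate, and the power sentence uses the correlation with baseline.

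**The case against.** The strongest objection is about weight. VFQ is one of many secondary endpoints, the trials are sized on acuity and endothelial cell loss, and the VFQ sentence sets no sample size, alpha or stopping rule. For DETECT I the shift is modest: with 72 per group the difference detectable with 80% power is (1.960 + 0.842) × 1.448 = 4.06 points, so that trial stays close to conventional 80% power for 4 points. The sentence also speaks of the study as a whole and makes no separate 90% claim for DETECT II. All of this stands and limits the consequence. It does not supply a comparison with 110 per group.

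The 10% loss is carried over from section 9.2. Section 5.5 reports complete 12-month follow-up in the pilot, so no loss is also a documented scenario. That is why both figures are shown; 90% is missed in either case.

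A pooled analysis might be set out in the SAP, which is not at hand. The finding is therefore only that the protocol describes none.

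A reader might infer three stronger things that the documents do not support:

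- **Adjustment for a post-operative score, or for one never collected.** The adjacent sentence and the schedule identify the covariate as baseline VFQ, so the label is a slip.
- **70% as the power of the Holm procedure in DETECT I.** The 0.025 threshold applies to the smaller p-value only, so 70% is a lower bound for a comparison. The correction is across the factorial treatments and does not touch DETECT II.
- **VFQ in DETECT II should be reduced to estimation only.** That would change its inferential status, which a corrected group size does not require.

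**Conclusion.** The point holds as an inconsistent input. The 90% power claimed for 4 NEI-VFQ points belongs to a comparison that the protocol does not describe. For the comparisons it does describe, power is about 79% to 83% in DETECT I and about 39% to 43% in DETECT II, with the lower figure of each pair assuming 10% loss and the higher none. The differences detectable with 90% power are about 4.7 (4.5) and 7.7 (7.3) points respectively, with the no-loss values in brackets. These results rest on the pilot SD of 10.1 and correlation of 0.51 applying to both trials, on a baseline-adjusted analysis, and on nominal two-sided alpha 0.05.

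It would be wrong to conclude that either trial is too small for its purpose. The primary sample sizes do not depend on this sentence.

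**What to change.** In section 9.4.3, replace the single VFQ power statement with one for each trial and state the loss assumption:

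- **DETECT I:** 80 per group; with 10% loss, about 79% power for 4 points, or 90% power for about 4.7 points. Note that this is at nominal alpha 0.05, and that power is about 70% if a comparison has to pass the first Holm step at 0.025.
- **DETECT II:** 30 per group; with 10% loss, about 39% power for 4 points, or 90% power for about 7.7 points.

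If a pooled comparison was in fact intended, the protocol should describe it and say how the different populations and comparators are handled.

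As a minor correction, change the covariate label to *baseline VFQ (Visit 1)*, in line with the following sentence and the schedule of activities.

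The cost is protocol wording and a less favourable stated figure. No patients, visits or measurements are added.

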The NEI and the US Food and Drug Administration recommend that vision-related quality of life measures be used to assess interventions in ophthalmology. This has become particularly important in an era of limited health care resources. DETECT-TES found both a clinically significant and statistically significant improvement in vision-related

DETECT

Version 5.0
21 March 2023

quality of life as measured by the NEI-VFQ at 12 months in those undergoing either DMEK or UT-DSAEK ($P < 0.001$). Given that a 4-point change in overall VFQ score is considered to be a small clinically significant change, an increase of approximately 13 points from baseline on average is remarkable.⁴² Interestingly, however, it was unable, to find a difference in vision-related quality of life between treatment arms. This may be related to a lack of power to find a difference given the small numbers in the study, however, *if there is no improvement in vision-related quality of life among DMEK patients, the advantages of DMEK over UT-DSAEK are less compelling.*⁴³

The number of DMEK procedures performed each year in the US has increased dramatically in recent years. According to the Eye Bank Association of America, DMEK accounted for less than 15% of endothelial keratoplasties in the US in 2015, whereas DSAEK accounted for approximately 50% of all corneal transplants. In 2017 the number of DMEK surgeries increased to 26% of all endothelial keratoplasties and in 2018 DMEK surgeries increased by another 41%.⁴⁴ The increase is likely due to a combination of factors including the results of DETECT-TESS, improvements in eyebank prepared tissue (pre-stripped, pre-punched, pre-loaded), and standardization of surgical techniques.^{11,45} DMEK may provide better visual acuity outcomes in carefully selected patients and at specialized centers; however, it may also carry more risks and a higher cost to society. Understanding the long-term implications of the potential ECL identified in DMEK on graft survival will be crucial to protecting the donor pool. The role of adjuvant topical selective ROCK-inhibitors in supporting endothelial cell health remains unclear. *Our proposed multi-center outcome-masked randomized placebo-controlled trial will profoundly impact clinical practice with regard to these surgical and adjuvant medical therapies. It also has the potential to yield longer-term outcome data, although that is beyond the scope of this 5-year funding.*

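### The NEI-VFQ power claim assumes 110 patients per group, a size no randomised comparison has; power for 4 points is about 79% in DETECT I and 39% in DETECT II, not 90%

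*Protocol*

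**What the plan says.** The vision-related quality of life paragraph of Protocol section 9.4.3 compares NEI-VFQ-25 between groups at 3 and 12 months by linear regression on baseline and assignment. It states that the study is "sufficiently large to detect a difference in NEI-VFQ of 4 points", at a two-sided 5% alpha, with "90% power, 110 patients per group, outcome standard deviation of 10.1 and correlation between baseline and follow-up of 0.51". The SD and correlation come from the pilot.

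Section 9.2 gives the only group sizes in the protocol. For each DETECT I comparison it reads "With 80 patients per group (160 total"; for DETECT II it reads "With 30 patients per group (60 total". Both calculations allow for 10% loss to follow-up. Section 9.4.2 specifies the primary models separately for the two trials.

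Section 2.2 describes a 4-point change in VFQ as small but clinically significant, says the pilot's failure to separate the arms on VFQ may reflect low power, and adds that "if there is no improvement in vision-related quality of life among DMEK patients", the case for DMEK over UT-DSAEK is weaker.

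**The concern.** The synopsis enrols 160 participants in DETECT I and 60 in DETECT II, 220 in all, and 220/2 = 110. The VFQ sentence therefore treats two trials as one two-arm trial. There are two ways to reach 110 against 110, and neither is a randomised comparison of one factor:

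- DMEK (80 + 30) against a mixture of UT-DSAEK (80) and DSO (30).
- Ripasudil (80 + 30) against placebo (80 + 30). The DETECT II part of this is DSO with ripasudil against DMEK with placebo, so drug and surgery cannot be separated there.

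The trials also differ in eligibility (section 5.1) and in steroid schedule (section 6.1.2), and in DETECT II the steroid schedule differs by arm.

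What is at stake is interpretation. Section 3 says VFQ will help decide whether differences in BSCVA or cell density matter clinically, and section 2.2 ties the appeal of DMEK to it. A reader who trusts the 90% may take a null VFQ result as good evidence against a 4-point difference, which neither trial can supply with that assurance. Pooling to reach 110 would change what is being estimated.

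**Working it through.** **Inputs.** From section 9.4.3: difference 4 points, two-sided alpha 0.05, SD 10.1, correlation 0.51, 110 per group. From section 9.2: 80 per group (DETECT I), 30 per group (DETECT II), 10% loss, and an ANCOVA sample size formula.

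**Adjusted SD.** 10.1 × √(1 − 0.51²) = 8.69.

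**Reproducing the plan's figure.** The number needed per group for 90% power is 2 × (1.960 + 1.282)² × 8.688² / 4² = 99.1. Taking 10% off 110 leaves 99 evaluable per group. With power = Φ(4/8.688 × √(n/2) − 1.96), n = 99 gives Φ(3.24 − 1.96) = 90.0%. The stated 90% is therefore correct arithmetic for 110 randomised per group with 10% loss. With no loss, n = 110 gives 92.7%.

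The same 10% convention reproduces the BSCVA claims in section 9.2: DETECT I, 0.11 logMAR, SD 0.2, n = 72: 91.0%; DETECT II, 0.13 logMAR, SD 0.147, n = 27: 90.1%. Applying it to VFQ is like for like.

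**At the real group sizes.** Detectable difference at 90% power = 3.2415 × 8.688 × √(2/n).

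| Comparison | Evaluable per group | Power for 4 points | Detectable at 90% power |
|---|---|---|---|
| As stated, 110 less 10% | 99 | 90.0% | 4.00 |
| DETECT I, no loss | 80 | 82.9% | 4.45 |
| DETECT I, 10% loss | 72 | 78.9% | 4.69 |
| DETECT II, no loss | 30 | 43.0% | 7.27 |
| DETECT II, 10% loss | 27 | 39.4% | 7.66 |

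Using the t distribution moves the 10%-loss figures only slightly, to 78.3% and 38.2%.

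**Multiplicity.** These figures use the sentence's own 5% alpha. Section 9.4.3 also applies a Holm-Bonferroni correction across the two factorial treatments. At a first-step alpha of 0.025, DETECT I power would be 69.9% (n = 72) or 74.9% (n = 80). The group-size error stands whichever alpha is used.

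**If ripasudil were pooled.** DETECT II would supply 30/110 = 27% of each arm. In a crude pooled difference with no term for surgery, each VFQ point of true difference between DSO and DMEK would shift the ripasudil estimate by about 0.27 point.

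**The case against.** The best defence is that the calculation is right for the inputs given and that the protocol does not forbid pooling. Aim 1 is worded jointly, with DMEK set against UT-DSAEK or DSO, and the VFQ sentence speaks of the study rather than of each trial. DMEK against all its comparators would be 110 against 110, and an SAP not shown might define that. It is true that the error lies in the group size and not in the formula. But a joint wording of the aim is not a pooled analysis. The protocol models its primary endpoints trial by trial and describes no pooled VFQ comparison. An SAP could add such an analysis; it could not give either trial 110 per group.

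Other points stand in part:

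- The VFQ sentence does not mention loss, and the pilot had complete 12-month follow-up. Without loss the powers are 83% and 43%, still below 90%.
- The 0.27-point shift applies only to a crude pooled contrast. A model with its own term for DSO would remove it, and the protocol does not say that VFQ will be pooled.
- Section 2.2 is hedged about the pilot, and no decision rule depends on VFQ. The harm is a risk of misreading, not a flaw in a primary analysis.
- The DETECT I shortfall is modest; the large one is in DETECT II, which was sized for BSCVA.

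**Conclusion.** The concern holds. The stated 90% power for 4 points belongs to a comparison of 110 against 110 that neither trial contains. After 10% loss, power is about 79% in DETECT I and 39% in DETECT II; with no loss it is 83% and 43%. The chance of missing a true 4-point difference is therefore about 1 in 5 in DETECT I and 3 in 5 in DETECT II, not 1 in 10.

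These figures assume that the pilot SD of 10.1 and correlation of 0.51 apply in both trials, a 5% two-sided alpha, and baseline-adjusted regression. VFQ is a secondary endpoint, so the sample sizes and primary analyses are unaffected. The claim should be corrected because it bears on how a null VFQ result would be read.

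**What to change.** In section 9.4.3, state that VFQ is analysed within each trial, and replace the power sentence with the delivered figures:

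- DETECT I, 80 per group: about 79% power for 4 points after 10% loss; 90% power for 4.7 points.
- DETECT II, 30 per group: about 39% power for 4 points after 10% loss; 90% power for 7.7 points.

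State the loss and alpha assumed. If a pooled analysis really is intended, it should instead be prespecified and justified, with the comparison named, the analysis stratified by trial, and DSO given its own term. It would then be a supplement to the within-trial results.

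It would also help to say that the VFQ confidence interval will be read against 4 points before the arms are called similar. That is good practice beyond the correction itself.

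The cost is a short edit and a less favourable stated power. No extra patients or visits are needed.
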